4.2 Registration Process for DF/HCC and DF/PCC Institutions

DF/HCC Standard Operating Procedure for Human Subject Research Titled *Subject Protocol Registration* (SOP #: REGIST-101) must be followed.

5. TREATMENT PLAN

5.1 Treatment Regimen

Following registration, participants will be randomized in a 2:1 ratio to either Arm A: a combination of Radium-223 and pembrolizumab or Arm B: Radium-223 alone.

Patients will be stratified based on:

- Baseline alkaline phosphatase <220 or ≥ 220
- Volume of bone metastases (high: ≥ 4 bone metastases including one beyond the axial skeleton vs. low: <4 bone metastases)
 Based on CHAARTED (ECOG 3805) criteria²⁴

Given the varied dosing of the two agents, we will refer to weeks on study instead of cycles.

Radium-223 55kBq/kg (1.49 μ Ci)/kg will be administered intravenously (IV) slowly over 1 minute every 4 weeks for a maximum of 6 doses. Weight used for dosing should be based on institutional standards. Radium-223 will be administered in the nuclear medicine suite at DFCI and at the corresponding department for participating investigational sites.

Pembrolizumab will be given only to patients randomized to the investigational arm (Arm A). Pembrolizumab will be given at a dose of 200mg intravenously every 3 weeks. It will be administered in the Yawkey Infusion Center at DFCI and at the corresponding department for participating investigational sites.

Treatment with both agents will be administered on an outpatient basis. Reported adverse events and potential risks are described in Section 7. No investigational or commercial agents or therapies other than those described below may be administered with the intent to treat the participant's prostate cancer.

No dose modifications will be made for either agent. If study agents are held for more than 12 weeks (for pembrolizumab) or 8 weeks (for Radium-223) due to study drug-related toxicity, the patient should be discontinued from the offending agent. Patients may continue on either agent alone if tolerating.

Agent	Premedication	Dose	Route	Schedule
Pembrolizumab	None unless	200mg	IV 30 minutes	Every 3 weeks (21 +/-3
	prior reaction;	(diluted	-5 min/+ 10	days)
	(see Table 6)	per	min	
		institution		*Should be given prior
		al		to radium on days
		guidelines		when they are given
		/package		together.
		insert)		
Radium-223	None	55kBq/kg	IV over 1	Every 4 weeks (28 +/-
		(1.49µCi)/	minute or	7 days) for 3 doses
		kg	longer per	followed by a break
			institutional	until radiologic disease
			standards	progression. Then the
				last 3 doses will be
				given every 4 weeks
				(28 +/-7 days)

Table 3: ARM A - Combination Investigational Arm

*Lupron/GnRH agonist or antagonist should be continued unless intolerable or discontinued for other safety reasons.

**Adhering to the schedule should be encouraged, and the 7 day window should not be utilized to give pembrolizumab and radium-223 on the same day for scheduling convenience.

Order of Administration – In the combination arm, pembrolizumab should be administered prior to radium-223 on days when both are given on the same day. No minimum time is required between the administration of drugs.

Table 4: ARM B - Control Arm

Agent	Premedication	Dose	Route	Schedule
Radium-223	None	55kBq/kg	IV over 1 minute	Every 4
		(1.49µCi)/kg	or longer per	weeks (28
			institutional	+/- 7 days)
			standards	for 6 doses

*Lupron/GnRH agonist or antagonist should be continued unless intolerable or discontinued for other safety reasons.

Trial treatment should begin on the day of randomization or within 7 days after randomization.

The Pharmacy Manual contains specific instructions for the preparation of the pembrolizumab infusion fluid and administration of infusion solution (Section 8.1).

5.2 **Pre-Treatment Criteria**

5.2.1 Cycle 1, Day 1

Pre-Treatment Criteria for C1D1. D1 dosing criteria of subsequent cycles (2 and beyond) should follow Section 6 guidelines:

C1D1 labs must meet the following criteria prior to treatment but do not need to re-meet eligibility criteria:

- Absolute neutrophil count \geq 1,500/mcL
- Hemoglobin ≥10g/dL *transfusions and/or erythropoietin supplementation permitted
- Platelets $\geq 100,000/mcL$
- Total bilirubin ≤1.5x institution's upper limit of normal (unless known Gilbert's syndrome)
- AST(SGOT)/ALT(SGPT) $\leq 2.5 \times$ institutional upper limit of normal ULN
- Creatinine clearance ≥30 mL/min/1.73 m² for participants with creatinine levels above institutional ULN. (*Note: creatinine clearance should be calculated per institutional standard*)
- If screening assessments have been done within 72 hrs prior to C1D1, they may be used in lieu of repeat C1D1 assessments (e.g., labs, ECOG, exam).

5.2.2 Subsequent Cycles

- Day 1 complete metabolic panel and complete blood count (CBC) with differential must be reviewed by study staff prior to treatment to ensure they meet criteria as detailed in Section 6
 - Other labs such as thyroid function tests that may take longer to result do not have to be reviewed prior to the dose
- CBC with differential should be obtained prior to each dose of radium-223 or pembrolizumab and doses given only if eligible per guidelines in Section 6
- Day 1 assessments may be performed within 72 hours prior to study drug administration.

5.3 General Concomitant Medication and Supportive Care Guidelines

If there is a clinical indication for medications or vaccinations specifically prohibited in the exclusion criteria, discontinuation from trial therapy or vaccination may be required. The investigator should discuss any questions regarding the use of these agents with the PI who will discuss with the Merck Clinical team as needed. The final decision on any supportive therapy or vaccination rests with the investigator and/or the subject's primary treating physician.

5.3.1 Acceptable Concomitant Medications

All treatments that the investigator considers necessary for a subject's welfare may be administered at the discretion of the investigator in keeping with the community standards of medical care. All concomitant medication will be recorded on the case report form (CRF) including all prescription, over-the-counter (OTC), herbal supplements, and IV medications and fluids. If changes occur during the trial period, documentation of drug dosage, frequency, route, and date may also be included on the CRF.

All concomitant medications received within 28 days before the first dose of trial treatment and 30 days after the last dose of trial treatment should be recorded. Concomitant medications administered after 30 days after the last dose of trial treatment should be recorded for SAEs and ECIs as defined in Section 7.2.

Treatment with non-conventional therapies and vitamin/mineral supplements is acceptable provided that, in the opinion of the investigator, such treatment will not interfere with study treatment and the trial endpoints. If they do, the subject may need to be discontinued from the trial and this should be discussed with the PI.

Subjects may receive standard of care for any underlying illness provided therapy does not interfere with study treatment and the trial endpoints.

In the event of neutropenia, anemia, or thrombocytopenia, subjects may receive appropriate supportive care (such as transfusion, biologic response modifiers such as G-CSF or GM-CSF, prophylactic antibiotics, antifungals and/or antivirals, hematopoietic growth factors).

If surgery is required during study drug treatment, the surgeon needs to be notified that the patient has been treated with a radioactive product and adequate precautions for radioactive protection should be applied during the surgical procedure. The patient should continue with study treatment if considered safe in the treating investigator's opinion.

Radium-223 can be administered with concurrent osteoclast-targeting agents including bisphosphonates and denosumab if the patient is already on them for > 28 days prior to Day 1 of study treatment. These agents should not be started while the patient is on the study unless needed for the management of hypercalcemia or a skeletal-related event. If a patient has already been receiving an osteoclast-targeting agent prior to study entry, it may be continued or suspended during concurrent administration of radium-223 at the discretion of the treating investigator.

Consideration should be given to using concomitant bone health agents such as bisphosphonates on either arm of the study. Patients receiving bisphosphonates, denosumab, zoledronic acid or similar therapy prior to randomization may be maintained on this therapy during the study. Bisphosphonates denosumab, zoledronic acid or similar therapy can be stopped or started at the discretion of the investigator throughout the study.

5.3.2 **Prohibited Concomitant Medications**

Subjects are prohibited from receiving the following therapies during the Treatment Phase of this trial:

- Antineoplastic systemic chemotherapy or biological therapy
- Immunotherapy not specified in this protocol
- Investigational agents other than pembrolizumab
- Radiation therapy other than radium-223
 - Note: Patients may undergo palliative radiation to combat clinical (e.g., symptomatic) progression while on study if (1) the patient was achieving overall clinical benefit according to the treating investigator; and (2) the Principal Investigator has determined it acceptable to do so. Study drugs should be continued during radiation unless discussed with the PI that holding is in the best interest of the patient (e.g., concurrent toxicity concerns).
- Live vaccines within 30 days prior to the first dose of trial treatment and while participating in the trial. Examples of live vaccines include, but are not limited to, the following: intranasal influenza, measles, mumps, rubella, varicella/zoster, yellow fever, rabies, BCG, and typhoid vaccine.
- Systemic glucocorticoids are prohibited, with the following exceptions:
 - To modulate symptoms from an event of clinical interest (ECI) of suspected immunologic etiology while on study.
 - Baseline systemic steroids ≤10mg of prednisone or its equivalent for nonautoimmune processes (e.g., COPD, physiologic replacement doses) if on stable dose and asymptomatic.
- Diethylstilbestrol, estrogens, saw palmetto or other preparations thought to have endocrine effects on prostate cancer are allowed if the patient has been on a stable dose for at least 8 weeks prior to C1D1.

Subjects who, in the assessment by the investigator, require the use of any of the aforementioned treatments for clinical management should be removed from the trial. Subjects may receive other medications that the investigator deems to be medically necessary.

The Exclusion Criteria describe other medications, which are prohibited in this trial.

There are no prohibited therapies during the Post-Treatment Follow-up Phase.

5.3.3 Supportive Care Medications

- Drugs needed for supportive care such as anti-emetics are permitted
- Steroids for nausea: dexamethasone, prednisone and other systemic steroids should be avoided, if possible, due to their immunosuppressive properties. If clinically indicated, steroid dose should not exceed 10mg of prednisone per day or equivalent.
- Subjects should receive appropriate supportive care measures as deemed necessary by the treating investigator. Suggested supportive care measures for the management of adverse events with potential immunologic etiology are outlined below. Where appropriate, these guidelines include the use of oral or intravenous treatment with corticosteroids as well as additional anti-inflammatory agents if symptoms do not improve with administration of corticosteroids. Note that several courses of steroid tapering may be necessary as symptoms may worsen when the steroid dose is decreased. For each disorder, attempts should be made to rule out other causes such as metastatic disease or bacterial or viral infection, which might require additional supportive care. These treatment guidelines are intended to be applied when the investigator determines the events to be related to pembrolizumab. If not thought related, care is per investigator discretion.

It may be necessary to perform conditional procedures such as bronchoscopy, endoscopy, or skin photography as part of evaluation of the event.

5.4 Criteria for Taking a Participant Off Protocol Therapy

Duration of therapy will depend on individual response, evidence of disease progression and tolerance. In the absence of treatment delays due to adverse event(s) or the scheduled break after the first 3 doses of radium-223 in arm A, treatment may continue for up to a total of 6 doses of radium-223 and up to 35 doses (24 months) of pembrolizumab if achieving clinical benefit and tolerating or until one of the following criteria applies:

- Disease progression
 - Arm A:
 - After 3 months on study therapy (generally week 12 re-staging scans)
 - If the patient has stable disease or better, they will start on a radium-223 break, but continue on pembrolizumab.
 - If there have been treatment delays, the break should not commence until at least 3 doses of radium are given unless the radium-223 is deemed intolerable/toxic.
 If pembrolizumab has been discontinued due to toxicity despite stable disease or better, radium-223 will be continued without a break, and study assessments will be conducted on the same schedule as Arm B.

- Due to the intricacies of assessing response/progression in bone only disease, in cases where the treating investigator feels the patient is clinically benefiting from the radium-223 and that a break would be harmful to disease control, omission of the break will be permitted on a case-by-case basis after discussion with the PI. These patients will be continued on the radium-223 every month without break as is standard of care. Study assessments during combination therapy will continue per the required data table in Arm A. Scans will continue to adhere to the study schedule (every 12 weeks). Alternatively, the patient or clinician may choose to stop study therapy and proceed with alternative systemic therapies at their discretion.
- If 2 or more new bone lesions ("unconfirmed progression") are present on initial scans and the patient has received all 3 initial doses, radium-223 should be continued until reassessment with confirmatory scans ≥ 6 weeks.
- If "unconfirmed progression" of nodal disease occurs, but no new visceral disease, the patient may continue on pembrolizumab and radium-223 until reassessment with confirmatory scans ≥ 6 weeks or be discontinued per treating investigator's discretion.
- For patients with unconfirmed bone or nodal progression who continue on study therapy after initial restaging scans (~12 weeks), if subsequent scans (at least ≥ 6 weeks from initial scans) show:
 - The disease has stabilized or improved: they may continue on study therapy until disease progression or until intolerability/toxicity precludes further administration.
 - Continued radiologic progression per RECIST v1.1 or PCWG2: the patient should be discontinued from study therapy. If the treating investigator believes the patient is clinically benefiting, continuation of one or both study drugs may be permitted upon discussion with PI.
- If there is evidence of new visceral disease at any point, the patient should be discontinued from both agents.
- For all subsequent scans of patient who commence on radium-223 break:
 - If the patient continues to have stable disease or better, they will continue on pembrolizumab alone.
 - If the patient went on radium-223 break, it may be restarted:
 - Whenever the patient meets progressive disease criteria per

protocol as long as there is no new visceral disease. No confirmatory scans are required unless the treating investigator prefers to wait to confirm before restarting. The rationale to allow restarting of radium-223 in patients who are progressing in the nodes is the possible role of radium-223 as an immune modulator that may help stimulate the immune response to pembrolizumab.

- In cases where treating investigator feels that patient would clinically benefit from restarting radium-223, even though not technically progressing by RECIST v 1.1 or PCWG2, will be discussed and permitted only on a case-by-case basis with the PI.
- If the patient meets protocol criteria for disease progression on the next scheduled scans after restarting radium-223 (and has received at least 2 more doses of radium-223), they should be discontinued from study therapy. If they do not meet these criteria or treating investigator believes they are clinically benefiting, they may be permitted to continue on a case-bycase basis after discussion with the PI. Similarly, if treating physician feels the patient is clinically progressing prior to 2 more doses of radium-223, the patient can be discontinued from study therapy.
- If patient has signs of new visceral disease at any time meeting RECIST v1.1 criteria, they will be discontinued from study therapy.
- For subsequent scans of patients who do not commence on radium-223 break:
 - If the patient continues to have stable disease or better, they will continue on combination study therapy.
 - If scans show progressive disease per protocol criteria, they should discontinue therapy. In cases where treating investigator feels that the patient would clinically benefit from continuing study therapy even though they are technically progressing by RECIST v1.1 or PCWG2, continuation will be discussed on a case-by-case basis with the PI.
- Arm B
 - Continue on radium-223 until the patient meets protocol criteria for disease progression, up to a maximum of 6 doses.
- Intercurrent illness that prevents further administration of treatment

- Unacceptable adverse event(s)
- Participant demonstrates an inability or unwillingness to comply with the documentation requirements
- Participant decides to withdraw from the protocol therapy
- General or specific changes in the participant's condition render the participant unacceptable for further treatment in the judgment of the treating investigator
- Completed 24 months of uninterrupted treatment with pembrolizumab or 35 administrations of study medication, whichever is later. *Note: 24 months of study medication is calculated from the date of first dose.*

Participants will be removed from the protocol therapy when any of these criteria apply. The reason for removal from protocol therapy, and the date the participant was removed, must be documented in the case report form (CRF). Alternative care options will be discussed with the participant.

An ODQ Treatment Ended/Off Study Form will be completed when a participant is removed from protocol therapy. This form can be found on the ODQ website or obtained from the ODQ registration staff.

In the event of unusual or life-threatening complications, treating investigators must immediately notify the Overall PI,

5.5 Duration of Follow Up

Participants will have a follow up visit within 30 days of removal from protocol therapy (End of Treatment visit). Adverse event monitoring will continue through End of Treatment visit. Subjects who discontinue for reasons other than progressive disease will have post-treatment follow-up for disease status until disease progression, initiating a non-study cancer treatment, withdrawing consent or becoming lost to follow-up. Follow up scans are not required for patients who do not progress, but will be captured if possible. After documented disease progression each subject will be followed by telephone, chart review, or clinic visit for overall survival until death, withdrawal of consent, or the end of the study, whichever occurs first. Regardless of reason for discontinuation, patients will be followed every 6 months until death or 2 years after treatment discontinuation.

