L: Diagnostic CT chest and CT or MRI of the abdomen and pelvis and bone scan including SPECT/CT should be obtained at baseline and every 12 weeks (+/- 7 days). (NOTE: SPECT/CT will be done only at DFCI.) Scans should remain on an every 12 week schedule (+/- 7 days) even if dose delays occur.

M*: Correlative immune studies: will be obtained and transported overnight at room temperature to the [name] Lab at UCSF. Samples for immune studies will be done at week 1 (pre-dose), week 5, week 9, week 13, week 21 and at the time of progression for those patients still on study.

N: Bone biopsy: archival tissue is permitted for baseline analysis. IR guided bone biopsy will be done at week 8 (+3 weeks) after the second dose of radium-223. If the second dose cannot be given for safety reasons, biopsy should still be performed within the window detailed here.

O: Blood samples for cell free DNA (cf-DNA) will be performed at treatment initiation (week 1, pre-dose), on treatment (week 5 and 13), and at time of progression.

P: Quality of life, pain and analgesic use will be measured via the FACT-P (Appendix B), Brief Pain Inventory (Short Form) (Appendix C), and analgesic diary (Appendix D) prior to treatment, at week 5, 9, then every 6-8 weeks after week 9 (as schedules differ between the two arms), and at treatment progression/off study visit.

Q: After progression/treatment discontinuation, follow the participant for survival, receipt of next line therapies, and post-treatment SSEs every 6 months until death or 2 years after treatment discontinuation.

R: Arm A study assessments will continue based on the same schedule as detailed for weeks 1-13 when pembrolizumab is given alone (e.g., visits, labs, assessments every 3 weeks only). If radium-223 is resumed upon progression, assessment schedule and radium-223 + pembrolizumab dosing will resume based on the schedule detailed for weeks 1-13. Arm B study assessments and radium-223 dosing will continue based on the same schedule detailed for weeks 1-13 up to 6 doses without breaks except for toxicity/intolerance (Section 6.2).

Note: For both arms: Immune studies will follow the schedule detailed in footnote M*

S: End of Treatment visit should occur within 30 days after last study treatment.

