13. STATISTICAL CONSIDERATIONS

13.1 Study Design/Endpoints

This is an open label phase 2 trial that randomizes 45 mCRPC patients (2:1 ratio) to radium-223 plus pembrolizumab combination therapy or to radium-223 monotherapy. The primary objective is to compare the increase in immune CD8+ and CD4+ T cell infiltration levels from baseline to 8 weeks on treatment between the two treatment arms.

Primary Endpoint:

Difference in tissue immune cell (e.g., CD4+/8+T) infiltration in the bone metastasis biopsy specimens from baseline to 8 weeks on treatments in both the combination and monotherapy arms.

Secondary Endpoints:

- Safety and Tolerability: grade 3 or higher adverse events that are considered treatment related according to NCI CTCAE (version 4.0)
- Progression-free survival (PFS): is defined as the time from the first dose of study drug to the earlier of the first documentation of definitive disease progression [as

defined by Response Evaluation Criteria in Solid Tumors (RECIST version 1.1) and PCWG2] or death due to any cause. Participants alive without disease progression are censored at date of last disease evaluation

• Overall survival as defined in 11.1.8

Exploratory Endpoints:

- Clinical-based endpoints
 - Changes in PSA
 - PSA response: defined as decline ≥50% from baseline to 12 weeks of therapy and which has been confirmed with a second PSA at ≥ 3 weeks later
 - Time to PSA progression as defined in 11.1.9
 - Time to normalization of alkaline phosphatase (if initially elevated)
 - Time to decrease in alkaline phosphatase (if initially elevated)
 - Symptomatic skeletal events (SSEs): Rate of SSEs and time to first SSE
 - Changes in osteoblastic activity on bone scan (assessed using the quantitative SPECT/CT)
 - Changes in quality of life, pain, and analgesic use, and time to introduction of analgesics
 - Immune-based endpoints
 - Quantify the CD8, CD4, and FoxP3+ CD4 (Treg) cell infiltration in the bone biopsy specimens, and to subsequently quantify the CD8/Treg and CD4/Treg ratios
 - Change in circulating T cell clonality
 - Induction of IgG antibody response
 - Changes in PD-L1 expression and co-regulation of other immune checkpoints such as TIM-3, LAG-3, and PD-L2
 - Changes in immunosuppressive cell populations and cytokines (e.g., MDSCs, Tregs, TGF-β, and iNOS)
 - Change in serum chemokines: (e.g., CXCL9, CXCL10)

- Changes in soluble PD-L1 ([name] Lab assay)
- Genomic-based endpoints

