13.8 Analysis of Secondary Endpoints

Safety and Tolerability: All adverse events recorded during the trial will be summarized for the safety population. The incidence of events that is new or worsening from the time of first dose of treatment will be summarized according to system organ class term, severity (based on CTCAE version 4.0 grade), type of adverse event, and relation to study treatment. For the combination therapy, special interests include toxicities related to induction of immune phenomenon such as pneumonitis, colitis, and severe rash. The frequency of AEs will be summarized separately according to treatment arms, with 90% exact binomial confidence intervals (CI). The proportion of patients in each arm with grade 4 or higher AEs will also be reported with an exact binomial 90% CI.

Deaths reportable as SAEs and non-fatal serious adverse events will be listed by patient and tabulated by primary system organ class, and type of adverse event.

PFS and OS: The distributions of time to PSA progression, PFS and OS will each be summarized using the product-limit method of Kaplan-Meier according to treatment arms. Median times for each endpoint will be presented with two-sided 95% confidence intervals estimated using log(-log(survival)) methodology. Kaplan-Meier estimates of the endpoints at 6 or 12 months after treatment initiation may also be presented with two-sided 95% confidence intervals.

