13.11 Analysis of Exploratory Genomic Endpoints

Mutations in DDR genes can be seen in around 30% of patients with metastatic CRPC.³⁴ We hypothesize that presence of these mutations would sensitize tumor cells to the DNA damaging effects of radium-223 and result in a longer PFS. The study is planned to enroll 45 patients who will receive radium-223. Assuming 10% will not have adequate tissue for sampling, we estimate that we will have adequate samples from at least 40 patients available for the correlative study. Using a log-rank test with a one-sided type I error of 0.15, there is 80% statistical power to detect an improvement in median PFS from 6 months (patients without DNA repair mutation) to 12 months (patients with a DNA repair pathway mutation) corresponding to hazard ratio of 0.50 (Table 21).

Table	21:
-------	-----

Assumptions:							
• N=40 (ev	• N=40 (evaluable samples)						
Median I	PFS in non-mutated DNA repair grou	up = 6 mor	ths				
DDR	Targeted median PFS (mos)	ШD	N (PFS	D			
mutation prevalence	in patients with patients with DDR mutation	HR	event)	Power			
		0.5	26	0.8			
0.3	12	0.5	36	0.0			
0.3	13	0.46	36	0.85			
0.4	12	0.5	36	0.82			
0.4	13	0.46	35	0.87			

The distributions of PFS and OS will each be summarized using the product-limit method of Kaplan-Meier according to prevalence of baseline genomic alternations (e.g., with or without DNA repair mutation). Median times for each endpoint will be presented with two-

sided 95% CI estimated using log(-log(survival)) methodology. Log-rank test will be used to compare the median PFSs between the DDR mutation groups. Kaplan-Meier estimates of the endpoints at 6 or 12 months after treatment initiation may also be presented with two-sided 95% confidence intervals.

For the cfDNA analysis, patients will be dichotomized based on baseline tumor purity status into 2 groups: high (tumor purity >7.5%) vs. low (tumor purity \leq 7.5%). The cutoff choice was based on the prior study that demonstrated 7.5% to be the lower limit of accurate detection for tumor derived cf-DNA.⁵⁷ Kaplan-Meier estimates will be used to assess the distribution of PFS according to tumor purity status. Medians of time to PFS will be shown with two-sided 95% CIs.

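### Scheduled scans stop at about week 24 in Arm B but can run to 24 months in Arm A, so by-arm median and 12-month PFS are not comparable as planned

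*Combined protocol and SAP*

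**What the plan says.** Section 5.4 gives the Arm B rule: "Continue on radium-223 until the patient meets protocol criteria for disease progression, up to a maximum of 6 doses". Footnote R of the study calendar ties Arm B's assessments to those six doses. The calendar shows no radiologic evaluation in the End of Treatment column, and footnote Q asks sites, once treatment has stopped, to "follow the participant for survival, receipt of next line therapies, and post-treatment SSEs every 6 months". In Arm A, section 5.4 allows up to 24 months of pembrolizumab, and footnote L keeps scans on a 12-week cycle with a 7-day window either way.

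Section 5.5 says that patients who stop for a reason other than progression are followed for disease status until they progress, start another therapy, withdraw or are lost. The next sentence reads: "Follow up scans are not required for patients who do not progress, but will be captured if possible". All patients are then followed every 6 months until death or for 2 years off treatment.

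PFS counts death from any cause. Section 13.1 adds: "Participants alive without disease progression are censored at date of last disease evaluation". Section 13.8 covers PFS and OS by arm: "Median times for each endpoint will be presented with two-sided 95% confidence intervals", with 6- or 12-month Kaplan-Meier estimates as an option. Section 13.11 rests its genomic comparison on PFS in both arms pooled, tested by log-rank at 0.15 one-sided. Its claim is that "there is 80% statistical power to detect an improvement in median PFS from 6 months (patients without DNA repair mutation) to 12 months". Table 21 gives the supporting event counts.

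**The concern.** Progression in this trial is defined by imaging. Where imaging is scheduled for about 5.5 months in one arm and up to 24 months in the other, a by-arm PFS curve past week 24 describes two different things. In Arm A it is scan-detected progression or death. In Arm B it is whatever scans happen to be captured, plus deaths.

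The censoring rule makes this worse. After week 24, an Arm B patient who is alive with no further scan is censored at the last scan, but one who dies unscanned enters as an event at the death date. Nothing in sections 11.1.8, 13.1 or 13.8 says how to treat a death after a gap in assessment. Arm B's median and 12-month PFS could then be not estimable, or could partly be survival times set beside Arm A's progression times.

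The DDR comparison in 13.11 relies on Arm B for about a third of its patients, so its stated power also depends on progression being ascertained in that arm well past week 24.

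**Working it through.** **Last scheduled Arm B scan.** Six doses every 4 weeks fall at weeks 1, 5, 9, 13, 17 and 21. The End of Treatment visit is within 30 days of the last dose. Twelve-weekly scans therefore fall at about weeks 12 and 24. Week 24 is 24/4.345 = 5.5 months. Dose delays would move this later for some patients.

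**Arm B event-free at that scan.** The documents state no Arm B median. Section 13.11 gives 6 months for DDR-unmutated and 12 months for mutated patients, with prevalence 30%. Assume exponential PFS.
- All at a 6-month median: 2^(-5.52/6) = 0.53.
- 70/30 mix: 0.7 × 0.528 + 0.3 × 0.727 = 0.59. The mix has a median of about 7.3 months.

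**Chance that Arm B's median is reached on scheduled scans.** With 15 patients and no earlier censoring, at least 8 events are needed.
- Event probability 0.47: 7.1 events expected, P(8 or more) = 0.41.
- Event probability 0.41: 6.2 events expected, P(8 or more) = 0.24.

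**Table 21 reproduced.** Schoenfeld power = Φ(|ln HR| × √(E·p(1−p)) − z), with HR 0.5, p = 0.3, one-sided 0.15 (z = 1.036). At E = 36: 0.693 × √(36 × 0.21) − 1.036 = 0.869, power 0.81, against 0.80 stated. The table is broken in extraction and could also be read as 26 events in the first row, but 26 gives 0.72, so 36 is the intended figure.

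**What 36 events presuppose.** With all 40 patients followed for 24 months, the event-free share is 0.7 × 2^(-4) + 0.3 × 2^(-2) = 0.119, giving 40 × 0.881 = 35.2 events. Table 21 thus fits ascertainment of about 2 years in both arms.

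**No Arm B scan captured after week 24, later deaths not counted.** Of 40 patients, 26.7 are in Arm A and 13.3 in Arm B.
- Arm B: 13.3 × (1 − 0.588) = 5.5 events.
- Arm A scanned to 24 months: 26.7 × 0.881 = 23.5. Total 29.0, power 0.75.
- Arm A with every patient having an event: 26.7. Total 32.2, power 0.78.

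A log-rank simulation (27 and 13 patients, 12 mutated) gives the same pattern: 35.4 events and power 0.78 with both arms followed to 24.4 months; 29.3 events and 0.72 with Arm B cut at week 24; 32.4 events and 0.74 if Arm A is also followed without limit.

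**Late deaths added.** Take the 14.9-month median survival quoted in section 2.2.1 as applying from week 24, unrelated to DDR status (an assumption). The share dying within 2 years is 1 − 2^(-24/14.9) = 0.67. Of 13.3 × 0.588 = 7.8 Arm B patients event-free at week 24, about 5.3 add an event, so 29.0 becomes 34.3. Simulated power in that case is about 0.69. The count recovers but the power does not, because these events are dated at death and carry no DDR contrast under this assumption, while living patients leave the risk set at their last scan.

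**The case against.** Much of the case on the other side stands.
- Section 5.5 does promise disease-status follow-up to progression and capture of scans where possible, and section 11.1 states 12-weekly re-evaluation without limiting it to the treatment period. Zero later capture is a worst case. If half of Arm B has later scans captured, simulated power is about 0.75 with 33 events.
- The waiver of scans is not specific to Arm B. Arm A patients who stop without progression fall under it too, and those who stop pembrolizumab for toxicity move to the Arm B schedule. The arms differ in degree, through length of treatment, and not in rule.
- The 6-month median belongs to DDR-unmutated patients pooled over arms, so the Arm B figures are conditional.
- Study duration is a larger cause of shortfall. Accrual of 12 to 18 months plus 6 months of follow-up yields only about 26 to 29 events even with full scanning.
- No between-arm PFS test is planned, the DDR analysis is exploratory, and a median reported as not reached is ordinary output.

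A reader might infer that 36 events could never be reached, however long follow-up ran. The documents do not support that. Death is a PFS event, only living patients are censored, and survival is followed for 2 years off treatment. If all Arm A patients have events, about 3.8 of the 7.8 remaining Arm B patients need a later progression or death to reach 36. Survival medians of 11.3 to 24 months give totals of 36.1 to 38.2.

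None of this removes the comparability problem. Captured if possible is not a schedule, and events supplied by death after an unscanned interval are not the same measurement as scan-detected progression.

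**Conclusion.** The point holds as one about unequal ascertainment and not as a ceiling on events. Scheduled imaging covers about 5.5 months in Arm B and up to 24 months in Arm A, and section 5.5 both promises follow-up to progression and waives the scans that would show it.

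If Arm B's median PFS is about 6 to 7 months, 53-59% of the arm is event-free at its last scheduled scan, and the median is reached on scheduled scans with probability of about 0.24 to 0.41. Past that point, Arm B's median and 12-month PFS would mix progression with survival times.

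For Table 21, scan-based events would be about 29 to 32 if nothing later is captured in Arm B. Power would then be 0.75-0.78 by the Schoenfeld formula against 0.81 at 36 events, or about 0.72-0.75 simulated against 0.78. These figures assume exponential PFS, DDR status balanced over arms, and no dose delays. The primary biopsy endpoint is not touched. The change is a cheap improvement to a secondary summary and to an exploratory power statement.

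**What to change.** - **Section 13.8.** Make the by-arm PFS summary the Kaplan-Meier rate, or the restricted mean, over a horizon both arms are scanned to: the second scheduled scan at about week 24, with the time point set to admit its 7-day window (for example week 25). Present by-arm medians and 12-month rates only alongside the number of patients per arm with scans after treatment and the time of their last scan.
- **Sections 13.1 and 13.8.** State how a death after a gap without scheduled scans is handled. Censor at the last disease evaluation, at least as a sensitivity analysis.
- **Section 13.11.** Note that 36 events and 80% power assume that progression is ascertained in both arms well beyond week 24. Give 29-32 scan-based events and Schoenfeld power of 0.75-0.78 as the case in which no later Arm B scan is captured, not as the expected count. Add that late deaths can raise the count without restoring the power.
- **Section 5.5.** Reconcile the promise of disease-status follow-up to progression with the sentence that waives scans.

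The cost is a shorter by-arm PFS summary and a less favourable stated power. The change needs no added scans or visits.
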